## **Methods: Assignment of interventions**

### Sequence generation

The curriculum for the Medical Humanities course is organized in three seminar groups, to which students are normally assigned in alphabetical order. For the purposes of this research, we will use a computer program ([www.randomisation.com](http://www.randomisation.com), permuted block method) to randomly assign students to one of the three groups and this list will be posted on the course web-site, as is usual practice for courses at the School.

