### Trial design

We will conduct a randomized control trial (RCT) with three different formats of the same systematic review summary (infographics, PLS and scientific summary). The content of these three formats is based on the same systematic review, but the ways of data presentation will differ: visual presentation in plain language, plain language, and scientific language. The trial will be performed at the beginning of the 2016/2017 academic year, with physicians as participants. The trial will be voluntary and anonymous. The survey will consist of 4 parts: 1) demographic data, 2) one format of the summary (randomly assigned), 3) comprehension test

of the information given in the summary, 4) accessibility of information and overall satisfaction with the given summary assessed by survey and 5) health numeracy test. All materials will be in Croatian. The materials used in this research will be assessed by experts in order to confirm face validity of the survey.

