## **Methods: Participants, interventions, and outcomes**

### Setting and recruitment

The trial will be performed online using SurveyMonkey software (A/B testing method).

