### Eligibility criteria

Eligible participants will be medical doctors in any specialty or field of work. Authors will make a list of publicly available e-mail addresses of doctors—clinical researchers from the School of Medicine and University Hospital Center in Split to make an email list of potential participants

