### Outcomes

The results for each participant will be the sum of correct answers at the knowledge test as the primary outcome, while secondary outcomes will be the number of correct answers on health numeracy and the scores on Likert-type scales for accessibility and satisfaction.

a) Demographic characteristics

Participants will first provide information about their gender, age, knowledge about or prior experiences with Cochrane reviews and Cochrane Library, obtained specialization or PhD.

b) Primary outcome: Understanding the information from the review summary

The primary outcome of the study is the score on a knowledge test with ten questions about information contained in all three forms of presentation. The questions will focus on understanding the benefits and risks of the intervention and the quality of evidence described in the systematic review.

Each correctly answered question will be awarded one point, with a maximum of 10 points. Prior research on PLSs (Vandvik et al., 2012) used multiple choice questions with a single correct answer to assess understanding of PLS. However, multiple choice questions are closed questions and the correct answer may provide a visual reminder to the participant and thus do not measure real understanding of the material (Choi & Pak, 2005). In order to reduce this measurement bias, we will use open questions to assess knowledge of the participants.

c) Secondary outcomes

C.1. Reading experience: This section of the survey will include 5 questions about the experience of participants about the text they read, measured on a 10-point Likert type scale, where 1 means *do not agree at all* and 10 means *fully agree*. The total score is the sum of scores on all five answers (maximum 50).

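### The plan contradicts itself on who is enrolled, how they are reached and how the arms are formed, and its only sequence-generation text cannot be applied to the eligible physicians

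*Combined protocol and SAP*

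**What the plan says.** All references are to the combined protocol and SAP.

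- **Who and how reached.** Trial design plans the study "with physicians as participants" and adds: "The trial will be voluntary and anonymous". Eligibility criteria agrees: "Eligible participants will be medical doctors in any specialty or field of work". Contact is through a list of public e-mail addresses of doctors described as "clinical researchers from the School of Medicine and University Hospital Center in Split".
- **Where and how assigned, online text.** Setting and recruitment: "The trial will be performed online using SurveyMonkey software (A/B testing method". Trial design says that one format is given at random.
- **Where and how assigned, course text.** Participant timeline has School of Medicine participants tested at a first course and School of Humanities participants tested in a psychology course. Sequence generation starts from the three seminar groups of a Medical Humanities course and uses a permuted-block program "to randomly assign students to one of the three groups and this list will be posted on the course web-site".
- **Concealment.** Concealment of allocation says that participants will not know their allocation because the invitation describes a study of readability.
- **Dropout.** Data Management expects little dropout because testing takes place in a compulsory lecture. It then excludes the results of anyone who quits part-way.
- **Outcome and its place in the survey.** "The primary outcome of the study is the score on a knowledge test with ten questions". Trial design lists this test third, followed by "4) accessibility of information and overall satisfaction with the given summary assessed by survey and 5) health numeracy test".
- **Lay persons.** Inferential statistics states the primary outcome as understanding by lay persons. Objectives reads the alternative hypothesis as showing that the scientific summary does not suit a lay audience.

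**The concern.** Random allocation is what licenses the comparison of the three formats. Here the one section that explains how the sequence is made refers to students, seminar groups and a course web page, none of which exists for a doctor answering an e-mailed link. A reader cannot establish from the plan how the eligible participants are to be allocated in detail, or what stops allocation from being foreseen.

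Two further rules depend on the course setting or on a different population. The reason for expecting little dropout disappears in a voluntary e-mailed survey, so the handling of people who leave is no longer a side issue. They leave after seeing their assigned format. If leaving depends on that format, comparing only those who remain is not protected by randomisation. Also, a conclusion about lay readers cannot come from a sample of doctors. Interventions itself describes the scientific summary as written for academics and practitioners, which is the audience the eligible doctors belong to.

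**Working it through.** There is no figure to reproduce. The check sets the sections side by side and follows the consequences.

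**Step 1: compare the two accounts.**

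| Item | Trial design, Setting and recruitment, Eligibility criteria | Participant timeline, Sequence generation, Data Management |
|---|---|---|
| Participants | Doctors in any field | Students (Sequence generation); course participants (Participant timeline) |
| How reached | Public e-mail addresses | Attendance at a course or lecture |
| Institutions | School of Medicine; University Hospital Center | School of Medicine; School of Humanities |
| Participation | Voluntary | During a compulsory lecture |
| Allocation | Random format; A/B testing named | Permuted-block list to seminar groups, posted on a course site |

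Each account names two institutions and they share only one. In the text available, no section describes separate cohorts or says which account governs.

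**Step 2: try to apply Sequence generation to the eligible doctors.** Seminar groups and a posted course list have no counterpart for them. Permuted blocks could be used, for example by order of entry to the survey, but the plan does not say so. Trial design and Setting and recruitment together suggest that the platform assigns the format. Neither states that A/B testing generates the allocation, or whether it is simple or blocked.

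**Step 3: look for concealment.** Concealment of allocation describes masking of the study's purpose. It names no mechanism that keeps the next assignment unknown until a person is entered.

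**Step 4: follow the exclusion rule.**
1. The rule in Data Management has no limit on when the person leaves. As written it covers someone who finished the knowledge test and quit during a later part.
2. On the order in Trial design, accessibility, satisfaction and numeracy come after the test. The first item of Survey C2 looks back on the test questions, which supports that order for C2. Nothing comparable fixes the place of the other parts, and Trial design announces four parts but lists five.
3. Data Management blocks movement to the next page until the current one is complete. That prevents skipped items, not leaving. It does not say how items are divided into pages or when answers are stored.
4. So, if the test comes before the other parts and its pages are stored on submission, a later leaver has a complete primary score that the rule discards. If the test shares a page with later items, or nothing is stored until the end, there may be no score to keep.

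**Step 5: compare the lay wording with eligibility.** Only doctors are eligible and no section recruits lay persons. The outcome statement in Inferential statistics and the lay clause in Objectives therefore refer to people outside the sample.

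**The case against.** The strongest reply is that the intended design can be guessed. Trial design, Setting and recruitment, and Eligibility criteria agree with one another and point to assignment by the survey platform, so the course text could be leftover wording. That stands in part: it indicates which account to follow. It does not supply the type of randomisation or the concealment mechanism, and it leaves the only sequence-generation section wrong for the stated population.

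A second reply is that the handling of leavers would need attention in either setting. That is true. It belongs here because the plan's reason for treating dropout as minor depends on the lecture.

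Some stronger readings are tempting, but the documents do not support them:

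- **That the exclusion rule has a known size.** A reader might count 10 + 5 + 5 + 6 = 26 items after the summary, find 16 of them after the knowledge test, and treat that share as the loss. It counts items, not people, and says nothing about who leaves, when, or from which arm.
- **That primary scores are certainly observed and then thrown away.** This depends on part order and on page-by-page storage, which the plan does not state.
- **That the posted list reveals the format.** It would show group membership, not necessarily the format tied to each group.
- **That using SurveyMonkey itself rules out a classroom.** It could be used there. The conflict is in recruitment, contact and allocation.
- **That three populations are recruited.** Lay persons are named in the interpretation and the outcome statement, but are recruited nowhere.
- **That separate cohorts were never described.** This can be said only of the text available, since part of the document was withheld from it.

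**Conclusion.** Wrong as written. Within the available text, the plan gives irreconcilable accounts of who is enrolled, how they are reached and how the arms are formed, and Sequence generation cannot be carried out on the eligible doctors. The finding is categorical and rests on direct comparison of sections, so confidence in it is high.

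The consequence for leavers is real but unquantified. The rule as worded reaches people who completed the knowledge test. How many scores would be lost depends on part order, pagination, storage and a dropout rate, and the documents do not settle these. No numeric bias is claimed. A reader might also infer that the trial is not randomised. The text does not support that: both accounts intend random allocation, and what is missing is one stated method that fits the population. The lay wording is a simpler correction, but left alone it would allow a conclusion that the sample cannot support.

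**What to change.** 1. **Population, setting and allocation.** Reconcile Participant timeline, Sequence generation and the opening sentence of Data Management with Trial design, Setting and recruitment, and Eligibility criteria. Replace the course and posted-list text with individual automatic assignment to one of the three formats at survey entry. State whether it is simple randomisation or permuted blocks by order of entry.
2. **Concealment.** In Concealment of allocation, name automatic assignment at entry as the mechanism.
3. **If course cohorts are also intended,** describe each with its own eligibility, setting and allocation, and say whether the cohorts are analysed together.
4. **Leavers.** In Data Management, put the knowledge test on its own page or pages and save answers page by page. Keep everyone who completed the test in the primary analysis in the assigned arm, even if they left later. Report by arm the numbers assigned, leaving before or during the test, leaving after it, and completing.
5. **State the limit of this rule.** It reduces selection after randomisation but does not remove it, because people who leave before finishing the test are still excluded.
6. **Sample size.** That section counts people who finish the whole survey. Align its wording with the new primary analysis set.
7. **Lay wording.** In Inferential statistics, name the population actually enrolled. In Objectives, remove the lay-suitability conclusion unless lay participants are enrolled.

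The cost is mostly wording, a table of counts and minor survey set-up. The conclusion becomes narrower, the number analysed may differ between primary and secondary outcomes, and the invitation must say that answers already submitted will be used.

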### Concealment of allocation

The participants will not be aware of intervention allocation before and during the trial as they will be invited to participate in research about the readability of new Cochrane formats.

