### Blinding

Participants will not be blinded to type of format, but the authors who analyse the answers will be blinded to the type of formats.

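### The only sequence-generation text posts a student seminar-group list that does not fit the physician online trial; if it is used, nothing described conceals allocation from those who enrol or run the trial

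*Combined protocol and SAP*

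**What the plan says.** All references are to the combined protocol and SAP.

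- **Sequence generation** starts from a student course: "The curriculum for the Medical Humanities course is organized in three seminar groups, to which students are normally assigned in alphabetical order". For the research, the alphabetical rule is replaced by a computer-generated permuted-block list, which will "randomly assign students to one of the three groups and this list will be posted on the course web-site". No sentence says which seminar group receives which format, when the list goes up, or whether it names the format.
- **Concealment of allocation** states: "The participants will not be aware of intervention allocation before and during the trial". The reason given is that people are invited to a study on how readable new Cochrane formats are. No list-holder, release step or timing relative to agreement is described.
- **Blinding** states: "Participants will not be blinded to type of format". The authors who analyse the answers are blinded.
- **Trial design** says of participation: "The trial will be voluntary and anonymous". It names physicians as the participants.
- **Setting and recruitment** states: "The trial will be performed online using SurveyMonkey software (A/B testing method)". **Eligibility criteria** admits medical doctors and builds an e-mail list of them.
- **Participant timeline** and **Data Management** return to course-based testing: the first describes course sessions at two schools, the second the opening lecture of a compulsory course.

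**The concern.** Allocation concealment means that neither the person deciding whether to take part nor the person inviting them can know the next assignment before that decision is final. A group list on a course web-site is an open list. If the group fixes the format, whoever knows the link between the two can read off the arm of every listed person before any of them agrees.

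The primary comparison of knowledge scores depends on the arms being alike at entry. If participation varies by arm and willingness is related to the score, the arms differ for reasons other than format. Keeping the analysts blind does not help, because the selection happens before there are answers to mark. Adjusting for the few demographic items collected would remove only the part of the difference that those items capture.

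**Working it through.** The plan has no figure to reproduce here. The first part sets the texts side by side; the second is illustrative arithmetic.

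**1. Which trial does the list belong to?**

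| Feature | Trial design, Setting, Eligibility | Sequence generation, Participant timeline, Data Management |
|---|---|---|
| Participants | Physicians, medical doctors | Students, course attendees |
| Recruitment | E-mail list | Course enrolment |
| Delivery or assignment | SurveyMonkey A/B | Seminar groups, list on course web-site |

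These cannot both describe one trial. If the left column is right, the posted list may not apply, and the only description of the sequence is the phrase naming the A/B method. If the right column is right, the list is the allocation.

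**2. What follows if the list is the allocation?**

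- *Stated:* there are three seminar groups; membership is randomised for this research; the list is posted; participation is voluntary; participants see their format.
- *Inferred, not stated:* one format per seminar group. The text stands under the heading on assignment of interventions, with three groups and three formats. Without this link it would contain no assignment of format at all.
- *Inferred, not stated:* posting before testing. A seminar roster normally tells students which group to attend.
- *Not stated and not inferred:* publication of the group-to-format key.

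So group membership is public. Format is known to key-holders, and to a participant once one member of the same group has seen it. The concealment section speaks only of what participants know and says nothing about those who enrol or run the trial.

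**3. Illustration of selective participation.** Only n = 15 per arm and α = 0.05 come from the Sample size section. Assumed, and not in the plan: a fraction f of one arm (the least willing) declines, willingness is normally distributed and correlates ρ with the score, and the test is a two-sided pairwise t-test.

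Shift in SD units: d = ρ·φ(z_f)/(1 − f). For f = 0.2, φ = 0.280 and φ/(1 − f) = 0.350. For f = 0.3, φ = 0.348 and φ/(1 − f) = 0.497. The rejection rate with no format effect comes from the noncentral t with 28 df and noncentrality d·√(15/2).

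| ρ | f | d (SD) | Noncentrality | Error of nominal 5% test |
|---|---|---|---|---|
| 0.3 | 0.2 | 0.105 | 0.288 | 5.9% |
| 0.3 | 0.3 | 0.149 | 0.408 | 6.8% |
| 0.5 | 0.2 | 0.175 | 0.479 | 7.5% |
| 0.5 | 0.3 | 0.248 | 0.680 | 10.1% |

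Table 1 of the plan names Kruskal-Wallis or ANOVA, so these rates describe a pairwise comparison and not the planned overall test.

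**4. Illustration of session confounding.** This applies only if each group is tested in its own session, which the documents do not say. With an assumed intraclass correlation r, the between-group mean square is inflated by λ = 1 + 15r/(1 − r). The three-group ANOVA then rejects a true null with probability P(F(2,42) > 3.22/λ).

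| r | λ | Rejection rate |
|---|---|---|
| 0.02 | 1.306 | 9.7% |
| 0.05 | 1.789 | 17.8% |
| 0.10 | 2.667 | 30.9% |

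**The case against.** The strongest reply is that the list probably belongs to another trial. Three sections describe physicians reached by e-mail and assigned by A/B testing. In that trial there is no course web-site, seminar group or shared session, and the remedy proposed below is the delivery method already named. This largely stands, and it is why the mismatch comes first. It does not close the point: the section headed Sequence generation is current text, and without it the plan has almost no account of sequence or concealment.

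A second reply is that the two statements need not conflict for participants. Posting is described as normal course practice, so students would see an ordinary roster and could know their group without knowing its format. This also stands for participants before anyone in the group has seen the format. It does not extend to staff who hold the key.

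Third, selective uptake would not be invisible. If group equals arm, the posted list gives the number assigned to each, and uptake per arm can be compared with it. That could reveal a gap in numbers but would not fully correct the bias. The low dropout expected in Data Management concerns leaving during the trial, not declining to start.

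Finally, the refusal rates, correlations and intraclass correlations used above appear nowhere in the plan. This is accepted; they show scale only.

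**Conclusion.** The point holds in conditional form. The plan's only sequence-generation text describes a posted student list that does not match the physician online trial. If that list is used and group determines format, assignments can be known before participation to at least the staff who hold the key, and no described mechanism prevents this. Selective participation by arm is then possible.

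A reader might infer that every participant's format is known in advance, so that the stated concealment is simply false. The documents do not support that: they give no posting date, no explicit link from group to format and no publication of the key. A reader might also infer that each format is confounded with a session. That needs one separate session per arm, which is nowhere stated. Calling the whole trial open-label would also go too far, because the analysing authors are blinded.

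On the assumptions shown, the error of a nominal 5% pairwise test would be about 6–10%. If separate sessions were used, the overall ANOVA error would be about 10–31% for intraclass correlations of 0.02–0.10. Neither range is an estimate for this trial. The change should be made because it removes a route to selection bias at almost no cost.

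**What to change.** 1. In Sequence generation, remove the seminar-group assignment and the posted list. State that each participant is assigned individually by the SurveyMonkey A/B function, triggered after the participant has agreed to take part and completed the demographic page, with nothing published beforehand. Trial design already places demographics before the summary, so the order of the survey need not change.
2. Reword Concealment of allocation to describe this mechanism and to say that neither staff nor participants can see an assignment before it is made.
3. Reconcile Sequence generation, Participant timeline and Data Management with Trial design, Setting and recruitment, and Eligibility criteria, so that one population and one setting are described throughout.

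The cost is protocol wording and one setting in software already named. The small downside is that independent A/B assignment does not guarantee equal arms, so the survey would have to stay open until each arm has the stated minimum of 15 completers.
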